8 STATISTICAL AND DATA ANALYSIS

Our study's principal hypotheses will be tested as follows:

Hypothesis 1 will be tested by calculating the proportion of respondents completing the study, and the corresponding 95% confidence interval for this estimate, and examining whether the confidence interval lies completely above a value of 0.3 or not.

To test **Hypothesis 2**, comparisons between the average monthly symptom burden (measured by the monthly aggregate of symptom scores) resulting from no treatment/placebo/statin treatment periods will be made using a longitudinal multilevel model. The most basic model to test hypothesis 2 would be:

To test **Hypothesis 2**, we will calculate the nocebo ratio across all patients. This is to avoids attempting to analyse the pathological distributions that would arise for patient whose mean statin symptom score is close or less than their no treatment score, because the nocebo ratio becomes disruptively extreme. Combining the data

Confidential Page 14 of 22

SAMSON Protocol No: 1.4

Version 1.4 10th April 2020

across all patients to yield a single statin, placebo and no treatment symptom score allows a representative and interpretable nocebo ratio to be provided.

Hypothesis 3 is that the majority of patients will be taking statins, or have a non-side effect reasons for not doing so, at 6 months after study completion. This will be a descriptive statistic of the sample, which does not require inference of the population mean. No further statistical analysis is therefore necessary

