This statistical analysis plan (SAP), which is based on protocol Version 1.2 dated August 1, 2019, defines the methods and analyses that Imperial College London plans to use to analyze the data from the Self-Assessment Method for Statin side effects Or Nocebo trial (henceforth, SAMSON). This study adheres to the principles outlined in the Medicines for Human Use (Clinical Trials) Regulations 2004 (SI 2004/1031), amended regulations (SI 2006/1928), and the International Conference on Harmonisation Good Clinical Practice (ICH GCP) guidelines. It is being conducted in compliance with the protocol, the Data Protection Act, and other regulatory requirements as appropriate. If the protocol is subsequently amended, this SAP may be amended as well. Should the SAP and the protocol be inconsistent with respect to the planned analyses, the language of the SAP is governing.

2. Investigational plan

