6.1. Primary outcome (Hypothesis 2)

Hypothesis 2: Overall >50% of symptom burden is nocebo rather than pharmacological.

For the trial, all participants receive a smartphone or, if they prefer, the application can be downloaded to their existing phone. Access to the phone will allow them to record real-time daily documentation of symptoms experienced on a visual analogue scale of 0-100.

Participants will rate symptoms every day, with the daily scores averaged into a monthly score.

SAMSON STATISTICAL ANALYSIS PLAN

January 14, 2020

Page 6

Each participant receives four months (4×28 days) each of no medication, placebo, and active medication (i.e, statin). We represent the individual participant's symptom score data as follows:

$$\begin{array}{ccc} x_{0_1} & x_{p_1} & x_{s_1} \\ x_{0_2} & x_{p_2} & x_{s_2} \\ x_{0_3} & x_{p_3} & x_{s_3} \\ x_{0_4} & x_{p_4} & x_{s_4} \end{array}$$

$$\bar{x}_0 = \frac{\sum_{j=1}^4 x_{0_j}}{4} = \frac{\sum_{j=1}^4 ((\sum_{i=1}^{28} x_{0_{ij}})/28)}{4}, \bar{x}_p = \frac{\sum_{j=1}^4 x_{p_j}}{4} = \frac{\sum_{j=1}^4 ((\sum_{i=1}^{28} x_{p_{ij}})/28)}{4}, \bar{x}_s = \frac{\sum_{j=1}^4 x_{s_j}}{4} = \frac{\sum_{j=1}^4 ((\sum_{i=1}^{28} x_{s_{ij}})/28)}{4}$$

\bar{x} - mean symptom score for no medication, placebo, statin, i -day 1 to 28 of treatment month, j - treatment month 1 to 4

We assume no carry-over effect. Thus, the estimated mean of the effect of nocebo is calculated as follows:

$$\text{Mean nocebo effect} = \sum_{n=1}^N \left(\frac{\bar{x}_{p_n} - \bar{x}_{0_n}}{\bar{x}_{s_n} - \bar{x}_{0_n}} \right) / N$$

N = number of study participants

Because the study participants are independent of each other, the variance of the estimated mean can be calculated as the sum of variances of the individual participants:

$$\text{Variance of the mean nocebo effect} = s^2 = \sum_{n=1}^N s_n^2 = \sum_{n=1}^N \text{Var} \left(\frac{\bar{x}_{p_n} - \bar{x}_{0_n}}{\bar{x}_{s_n} - \bar{x}_{0_n}} \right)$$

To calculate the variance of the estimate, we use a Taylor series approximation, which is a function of the variance of the numerator, variance of the denominator, and the covariance of the two:

$$1) \text{Var}(\text{numerator}) = \text{Var}(\bar{x}_p - \bar{x}_0) = s_p^2 + s_0^2 - 2r_{s_p, s_0} s_p s_0$$

$$2) \text{Var}(\text{denominator}) = \text{Var}(\bar{x}_s - \bar{x}_0) = s_s^2 + s_0^2 - 2r_{s_s, s_0} s_s s_0$$

CONFIDENTIAL

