6.1.1. Missing and partial data for primary outcome

For the calculation of mean symptom score for particular treatment (statin, placebo, no medication) missing scores ($i < 28$) will be handled by only using study months that have at least 10 of daily symptom scores non-missing. We will perform sensitivity analyses using different thresholds for non-missing scores (such as 14 and 16 non-missing scores) and compare the percentage of missing symptoms scores during the 'pill' months (statin or placebo) versus 'no pill' months. We will assess the temporal pattern of missing symptom scores by comparing the percentage of missing scores at the beginning of the study to the percentages at later study months.

The nocebo effect for an individual participant will be calculated only if he or she has non-missing symptom scores for at least one month of each treatment ($j \geq 1$). If the participant has not recorded any symptom score for one of the three treatments ($j=0$ for statin, placebo, or no pill) the nocebo effect cannot be calculated, and the primary endpoint analysis will exclude that participant.

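### For Hypothesis 2 the SAP reports only a mean of individual nocebo ratios: no difference between statin, placebo and no treatment is estimated with a confidence interval, and protocol section 8 and SAP section 6.1 need reconciling

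*Protocol*

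**What the plan says.** Protocol version 1.4 (April 2020), section 8, gives two analyses for Hypothesis 2, one after the other. The first says that contrasts of monthly symptom burden "resulting from no treatment/placebo/statin treatment periods will be made using a longitudinal multilevel model". It continues "The most basic model to test hypothesis 2 would be", and no equation follows in the text available to us; it may have been lost when the PDF was read. The second starts afresh and says "we will calculate the nocebo ratio across all patients". The reason given is that individual ratios misbehave for a patient "whose mean statin symptom score is close or less than their no treatment score, because the nocebo ratio becomes disruptively extreme".

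The SAP (January 2020) describes itself as a plan "which is based on protocol Version 1.2 dated August 1, 2019". On precedence it states: "Should the SAP and the protocol be inconsistent with respect to the planned analyses, the language of the SAP is governing".

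SAP section 6.1 forms three condition means per participant and takes (placebo − none)/(statin − none) for each person. It averages these over participants ("the estimated mean of the effect of nocebo is calculated as follows") and tests the average with a t statistic. Section 6.1.1 counts a month if it has at least 10 daily scores and requires at least one such month of each condition. If a condition has none, "the nocebo effect cannot be calculated, and the primary endpoint analysis will exclude that participant". No requirement is placed on the size or sign of statin minus no treatment. The bootstrap fallback in 6.1 concerns the variance only.

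The rest of the SAP does not compare symptom scores between conditions. Section 6.2 covers two proportions, section 9 summarises adverse events by subject, and section 10 covers questionnaire correlations.

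**The concern.** The trial asks how much of the symptom burden the drug itself causes. A ratio answers in relative terms only. It does not say how many points the statin adds over placebo, how precisely that is known, or whether tablets raise symptoms over no tablet at all. If they do not, there is nothing to apportion and the ratio carries no information, yet it can still be computed and printed. Protocol section 8 recognises that the ratio breaks down when the denominator is near or below zero, but the SAP has no matching safeguard.

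There is also a conflict about what the Hypothesis 2 analysis is. The protocol names a multilevel comparison and a pooled ratio. The governing SAP has a mean of individual ratios, the quantity that protocol 1.4 says it wants to avoid.

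**Working it through.** **The plan's own figure.** Neither document gives a precision or power figure for any difference between conditions. The only Hypothesis 2 figure is in SAP section 4.1, for the ratio: N > (1.96 × 0.29/0.10)², stated as 36. The printed expression equals 32.3, so 33; a t quantile gives 35. The planned 50 and the 60 randomised exceed all of these, and nothing below depends on this figure.

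**1. The ratio hides the absolute effect.** Take excesses over no treatment of 10 points on statin and 9 on placebo: ratio 9/10 = 0.9, statin minus placebo 1.0 point. Take excesses of 1 and 0.9: ratio again 0.9, statin minus placebo 0.1 point.

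**2. What the ratio does with no side effect.** Assume equal true means and normal, independent, equal-variance monthly scores. Let v be the variance of a participant's condition mean.
- Var(placebo − none) = Var(statin − none) = 2v. Their covariance is v, because they share the no-treatment mean, so the correlation is 0.5.
- Cov(numerator − 0.5 × denominator, denominator) = v − 0.5 × 2v = 0. The ratio is then Cauchy with centre 0.5 and scale √(1 − 0.5²) = 0.866.
- An average of independent Cauchy variables has the same distribution, and so does the pooled ratio. For the SAP's estimator and the protocol's pooled one alike, P(estimate > 0.5) = 50%.
- The 95% range is 0.5 ± 0.866 × 12.71, or −10.5 to 11.5. The chance of falling outside 0 to 1 is 67%.
- Simulation (50 participants, four months per condition, 20,000 trials) gave 50.2% above 0.5 for the mean of ratios and 50.8% for the pooled ratio.
- Formal rejection of 0.5 in the same simulation, one-sided at 5% (the SAP gives no numerical alpha for Hypothesis 2), was 3.1% with a t-test on the sample SD of the ratios and 0% with the SAP's variance formula as written.

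**3. Who is left out of the ratio.** If the order of the 12 months is unrestricted, the chance of having met all three conditions after k months is 1 − 3C(8,k)/C(12,k) + 3C(4,k)/C(12,k).
- k = 3: 64/220 = 29%
- k = 4: 288/495 = 58%
- k = 5: 1 − 168/792 = 79%
- k = 6: 1 − 84/924 = 91%

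The remaining early leavers are excluded by SAP 6.1.1, although their months could enter a mixed model.

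**4. Precision of statin minus placebo.** Half-width = 1.96 × √[(SD_person² + 2 × SD_month²/4)/N]. The documents give neither SD, so these are assumed, with N = 60 and complete data.
- Month SD 8, person SD of the effect 4: 1.96 × √(48/60) = ±1.75 points
- Month SD 12, person SD 7: 1.96 × √(121/60) = ±2.78 points

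If only 30 participants contributed fully and partial data were ignored, the figures would be ±2.5 to ±3.9.

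**The case against.** Five points can be made for the plan.

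*A reader might infer that the SAP dropped a model the protocol had promised.* The documents do not establish that. The SAP rests on protocol 1.2, which we do not have. In version 1.4 the multilevel sentence is followed by a reasoned substitute, the pooled ratio, so the sentence may be residual text. What stands is that section 8 is unreconciled within itself and with SAP 6.1.

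*A reader might take the 50% as the chance of wrongly declaring Hypothesis 2.* It is not. The SAP requires a test to reject, and with no side effect that happens in about 3% of trials at most under the variants run. The 50% describes only the printed point estimate.

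*A reader might say that the pharmacological effect is never estimated.* That is too strong. The stated objective is a proportion, one minus the ratio is the drug's relative share, and SAP section 5 provides for descriptive means. What is absent is the effect in symptom points with an interval.

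*It is tempting to interpret the ratio only if statin minus no treatment is significant.* This selects trials with large denominators. With month SD 10, person SD 5, N = 60, a true 2-point effect and a true ratio of 0.5 (all assumed), about 43% of trials pass, and the median pooled ratio among them is 0.44, against 0.48 over all trials. A caution is preferable to a hard condition.

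*Excluding participants who lack a condition is a separate missing-data matter.* This is fair: a pooled ratio could also use their data, so the exclusion does not by itself call for a multilevel model.

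**Conclusion.** The point holds in limited form. As the governing SAP stands, symptom scores reach the Hypothesis 2 result only through a mean of individual ratios. None of the three pairwise differences has an estimate or interval, and nothing shows whether there is a total side effect to divide. A ratio of 0.9 is compatible with a drug effect of 1.0 point or 0.1 point. With no effect at all, the point estimate lands above 0.5 about half the time, without this amounting to a false-positive rate.

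The 50% rests on normal, independent, equal-variance monthly scores with no floor at zero; it needs no assumed SD. The precision of about ±1.8 to ±2.8 points is illustrative, because it rests on assumed SDs and complete data, and dropout would widen it. This should be corrected, but it does not invalidate the ratio as the trial's chosen measure.

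**What to change.** 1. Reconcile protocol section 8 with SAP section 6.1. State which Hypothesis 2 analysis is primary (multilevel comparison, pooled ratio or mean of individual ratios) and remove or complete the others. Update the protocol version on which the SAP is based.
2. Add to SAP 6.1 a mixed model of monthly mean score on condition (three levels), with random participant and participant-by-condition effects. Use all usable months of all randomised participants, including those whom 6.1.1 excludes from the ratio.
3. Report statin minus placebo, placebo minus no treatment and statin minus no treatment, each with a 95% interval, beside the ratio.
4. State that when the interval for statin minus no treatment includes zero (or lies below it), the ratio is read with caution as not reliably interpretable. Do not make this a hard condition for reporting it.

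The cost is SAP and protocol wording and one standard model on data the trial already collects. The price is that the caution may leave Hypothesis 2 without a clear reading if no total side effect is shown.

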8.1 POWER CALCULATIONS

Hypothesis 1: We hypothesise that of the patients enrolling for the study, 50% or more will complete the study. Our intention is to report the proportion of patients completing the study and its 95% confidence interval. Based on the binomial principle, $SE_p = \sqrt{p \cdot q/n}$, the number of patients planned after the calculation below (50) will permit this proportion to be stated with a 95% confidence interval of $\pm 1.96\sqrt{\frac{1}{2} \cdot \frac{1}{2}/50}$. Thus the proportion will be reported with a margin of error of $\pm 14\%$

or smaller. If the long-run proportion of patients who would finish the study is ~70%, then a sample size of 50 gives 85% power to detect this at the 5% significance level.

Hypotheses 2 and 3: These hypotheses address the sample of participants and not the population at large. They therefore do not need a sample size calculations.

9 MONITORING

9.1 RISK ASSESSMENT

This study is adopted by the Imperial Clinical Trials Unit (ICTU). ICTU will risk assess the study and undertake monitoring responsibilities relevant to the trial's estimated level of risk.

10 REGULATORY APPROVALS

10.1 CLINICAL TRIALS AUTHORISATION

The study will be performed in compliance with UK clinical trial regulations. Clinical Trial Authorisation from the Medicines and Healthcare products Regulatory Authority (MHRA) will be obtained prior to the start of the study. In addition, the Regulatory Authority must approve amendments (as instructed by the Sponsor), receive SUSAR reports and annual safety updates, and be notified of the end of the trial.

10.2 ETHICAL APPROVAL

Prior to enrolment of subjects, written approval from the REC must be obtained for named sites, the protocol and any amendments, the Patient Information Sheet and Consent Form, any other written information that will be provided to the subjects, any advertisements that will be used and details of any subject compensation. The study must be submitted for Site Specific Assessment (SSA) at Imperial College Healthcare NHS Trust. The Chief Investigator will require a copy of the Trust R&D approval letter before accepting participants into the study. The study will be conducted in accordance with the recommendations for physicians involved in

Confidential Page 15 of 22

SAMSON Protocol No: 1.4

Version 1.4 10th April 2020

research on human subjects adopted by the World Medical Assembly, 7th Version of the Declaration of Helsinki (2013). The REC will be sent annual progress reports, annual safety reports and will also be informed about the end of the trial within the required timelines.

10.3 INFORMED CONSENT

Prior to informed consent being received participants will be given ethically and trust approved version controlled information sheets regards the study and given at least 24 hours but preferably at least a week to read this information prior to consent.

For the pilot study the research nurse who is experienced in receiving informed consent for qualitative research will undertake the informed consent process with participants. Participants will be given the option of attending in-person or by telephone. If consent is undertaken in-person, written informed consent will be received from the participant prior to undertaking the interview and copy of the consent form will be given to the participant for their records. If a participant opts for a telephone interview, the participant information sheet, a separate telephone consent form and the questionnaires will be sent to the participant in advance of the telephone call. The study nurse will then receive verbal consent over the telephone prior to turning on the voice recorder and will sign the consent form. A copy of the completed telephone consent form will be sent to the participant. The voice recorder will only be turned on once verbal consent has been fully received and the study nurse will always seek permission of the participant prior to turning on the telephone voice recorder and then will also state clearly the voice recorder has been turned on and then start the interview.

For the main trial participants will be consented by the Research Fellow or Chief investigator/Principal investigator. The research fellow will be a cardiology SpR (MB BS MRCP); who will be able to assess mental capacity and understands the principles of informed consent.

Only participants who are able to fully consent to the study will be recruited. As there is an extra time commitment associated with the study, and much of the study is in addition to usual care, only participants who have capacity to refuse will be approached. There is no funding available for translation so people who cannot speak or write in English will be unable to participate. It will be highlighted to participants that they can withdraw their consent at any stage.

10.4 CONFIDENTIALITY

The Chief Investigator will preserve the confidentiality of participants taking part in the study and is registered under the Data Protection Act.

10.5 INDEMNITY

Imperial College London holds negligent harm and non-negligent harm insurance policies which apply to this study.

Confidential Page 16 of 22

SAMSON Protocol No: 1.4

Version 1.4 10th April 2020

10.6 SPONSOR

Imperial College London will act as the Sponsor for this study. Delegated responsibilities will be assigned to the NHS trusts taking part in this study.

10.7 FUNDING

The British Heart Foundation are funding this study. Travel reimbursement for site visits has been allocated.

10.8 AUDITS

The study may be subject to inspection and audit by Imperial College London under their remit as sponsor and other regulatory bodies to ensure adherence to GCP and the NHS Research Governance Framework for Health and Social Care (2nd edition).

11 TRIAL MANAGEMENT

11.1 TRIAL MANAGEMENT GROUP

A Trial Management Group (TMG) will be appointed and will be responsible for overseeing the progress of the trial and will include independent members.

The day-to-day management of the study will be co-ordinated through Imperial College London by research nurse [name], who will be supervised by research fellow [name] and Consultant Cardiologist [name].

The study has been adopted under the Imperial Clinical Trials Unit (UKCRC ID number 18).

11.2 DATA MONITORING COMMITTEE

A Data Monitoring Committee (DMC) will be convened to review safety data annually and advise the TMG if the trial should continue. A Charter will be devised to list the roles and responsibilities of the members.

12 DATA MANAGEMENT

Inform will be used to manage the data for the study. InForm is a validated data capturing system with a full audit trail.

13 ARCHIVING

Following the end of the study, when deemed practical, all essential documents will be archived for a minimum of 10 years as per Imperial College London guidelines.

14 PUBLICATION POLICY

We plan to disseminate the results of this study through publication in peer reviewed scientific journals, conference presentations and publication on Imperial College London website.

Confidential Page 17 of 22

16.1 APPENDIX ONE: PATIENT AND PUBLIC INVOLVEMENT FEEDBACK

National Institute for Health Research

Feedback from participant and public involvement group

· What are your initial feelings about the research?

"I think the study is very important as a lot of people have complained about certain types of statins prescribed. They have complained about muscle cramps and other adverse reactions.

"I felt a little uneasy. If I have already had side effects from taking statins I do not think I would want to restart even if it might help others in the long run. I would rather wait to see if findings from such research would benefit me. Some prospective participants might have a different view to mine and would be prepared to risk side effects again, especially if they were being monitored whilst on the trial and they knew they could pull out from trial. (In my own case I was started on a statin and felt really unwell but was then quickly changed to a different statin which up to now has shown no side effects) Good to see phone app technologies which might be useful"

"Potentially useful, but I will not volunteer to participate. Having had serious muscle problems with 20 mg Simvastatin, which stopped within a week of ceasing to take them, I consider it important to assess specifically the side effects. I seriously doubt the claim that studies of 80,000 ""showed no tendency to experience more unwanted side effects with statins than with a placebo drug."" Many diabetics contributing to the diabetes.co.uk/forum experience problems with statins."

"Very positive as there are lots of differing views about statins with non-medical people"

Do you think the research question is important?

"I suppose so, if statins have great benefits and it was found in evidence gathered already from 80,000 participants (referred to in info) that there was no tendency to experience more unwanted side effects with statins than placebo"

"Yes - hopefully participants will be better & specifically informed. I was not - apart from the small print in the leaflet. It may show whether other health conditions are

Confidential Page 23 of 22

23/07/2020, 14:08

SAMSON Protocol No: 1.4

Version 1.4 10th April 2020

affected by statins, or statins affect the health conditions - e.g. diabetes, blood glucose, dementia, blood pressure,"

"Yes as it clearly sets out the reasons for the research."

Do you feel that the treatment and assessment plan will be acceptable to the participants?

"For those wanting to take part, yes."

"Yes."

"I think as long as it is non-invasive, there should not be any concerns."

"Yes as it explains the procedure for the research clearly."

What issues do you think will affect people's decision to take part in the study?

"Some people might worry about using a Smartphone app, more elderly perhaps but others will embrace the technology. See box 1 re decision to take part after experiencing side effects. This can weigh heavily on a person if it affected day to day life and worries. However they might feel they have more monitoring and contact. I do generally think with more support and feedback some people would pursue taking statins. However in ordinary settings, you are prescribed and then don't have long enough to talk to a doctor or nurse about side effects etc. It's all well and good having these wonderful medications and maybe clinicians play down minor side effects even though they are more important to participants."

"The severity of side effects previously experienced."

"I cannot think of negative decisions."

Confidential Page 24 of 22

Version 1.4 10th April 2020

[figure not shown]
